### Concomitant therapy data collection

For therapy that the participant is receiving at the time of enrollment or receives during the study, including over-the-counter medications, authorized study personnel should collect

- the name of medication, vaccine, or therapy
- the reason for use, and
- dates of administration, including start and end dates.

For diabetes and lipid-modifying medications, collect dosage information including dose and frequency.

Non-study medications taken by study participants who have signed informed consent, but are not randomly assigned, will not be reported unless an SAE or AE occurs that the investigator believes may have been caused by a study procedure.

### 6.8.1. Medications with Approved Weight Loss Indication

#### Allowed usage of weight loss medication during the study

A participant may use a medication that promotes weight loss if they are on stable therapy 90 days prior to screening (Visit 1).

Allowed medications include, but are not limited to

- over-the-counter medications, including food supplements that promote weight loss
- liraglutide 3.0 mg
- orlistat
- sibutramine
- mazindol
- phentermine
- phentermine and topiramate combination
- naltrexone and bupropion combination, or
- semaglutide injection 2.4 mg.

### Prohibited usage of weight loss medication during the study

After screening (Visit 1), no prescription or over-the-counter medications that promote weight loss may be initiated or changes in dosage allowed.

#### 6.8.2. Chronic Systemic Glucocorticoid Medication

Chronic systemic glucocorticoid therapy is allowed for no more than one 14-consecutive day period during study treatment period.

This restriction does not apply to glucocorticoid therapy used as replacement therapy for adrenal insufficiency, or topical, intraocular, intranasal, inhaled preparations, and intra-articular injections.

#### 6.8.3. Antihyperglycemic Medications

This table shows the conditions for use of other antihyperglycemic medications.

Drug Class	Use during Screening or Lead-In	Conditions for Use after Randomization			
		During Treatment Period	Acute Therapy Treatment for up to 14 days	Rescue Therapy	During Safety Follow-Up Period
	Y = yes, if on stable therapy 90 days prior to screening. N = No	Yes, if on stable therapy 90 days prior to screening	N/A	Y b	Y c
Metformin a	Y		N/A	Y b	Y c
GLP-1 Ras	Y		N/A	Y b	Y c
DPP-4 inhibitors	Y		N/A	Y b	Y c
SGLT2 inhibitors	Y		N/A	Y b	Y c
Non-study daily basal insulins	Y	N	Yes, only if study basal insulin is temporarily discontinued	See Note d	Y
Non-study prandial insulin	Y	N	Yes, only if study prandial insulin is temporarily discontinued	Y	Y
Insulin mixtures	N	N	N	N	N
Meglitinides	N	N	N/A	N	N
Alpha-glucosidase inhibitors	N	N	N/A	N	N
Sulfonylureas	N	N	N/A	N	N
Thiazolidinediones	N	N	N/A	N	N

Abbreviations: DPP-4 = dipeptidyl peptidase-4; GLP-1 RA = glucagon-like peptide-1 receptor agonist; N = no; N/A = not applicable; SGLT2 = sodium-glucose cotransporter 2; Y = yes.

a Switching metformin manufacturer is allowed if the dosage is the same. Changing to a metformin formulation with a different action profile (that is, from short-acting to long-acting metformin) is not permitted.

- b For rescue therapy, concomitant antihyperglycemic medication doses may be increased if the dose is below maximum approved dose per country-specific label.
- c Participants can continue on these therapies but should not start a new class of therapy during the 5-week safety follow-up period.
- d Participants who require a non-study basal insulin as rescue therapy must discontinue study basal insulin therapy (LY3209590 or insulin glargine). The participant will remain in the study and follow procedures for the remaining study visits.

Dose adjustments of allowable non-insulin antihyperglycemic medications are permitted after randomization under the following circumstances:

- situations that require short-term treatment interruption consistent with the product labeling for each respective country
- situations that require dose adjustment or discontinuation per country-specific label, for example, in the case of reduced estimated glomerular filtration rate
- in the case of increased hypoglycemia risk during the treatment period (as described in Section 8.3.6), and
- for safety reasons at the discretion of the investigator.

Any changes in dose should be documented.

## 7. Discontinuation of Study Intervention and Participant Discontinuation/Withdrawal

Discontinuation of specific sites or of the study as a whole are handled as part of Appendix 1.

### 7.1. Discontinuation of Study Intervention

When necessary, a participant may be permanently discontinued from LY3209590 or insulin glargine. If so, the participant will remain in the study and follow procedures for remaining study visits, as shown in the SoA.

Participants who stop LY3209590 or insulin glargine permanently may receive another glucose-lowering medication. The new glucose-lowering medication will be recorded on the appropriate CRF.

A participant should be permanently discontinued from LY3209590 or insulin glargine if

- the participant becomes pregnant during the study
- the participant requests to discontinue LY3209590 or insulin glargine
- the participant is diagnosed with an active or untreated malignancy, except for successfully treated basal or squamous cell carcinoma
- the participant did not take insulin glargine for more than 21 consecutive days or missed more than 3 consecutive doses of LY3209590 at any time during the study, or
- in the opinion of the investigator, the participant should permanently discontinue LY3209590 or insulin glargine for safety reasons.

#### 7.1.1. Liver Chemistry Stopping Criteria

The study drug should be interrupted or discontinued if one or more of these conditions occur.

Elevation	Exception
ALT or AST >8x ULN	
ALT or AST >5x ULN for more than 2 weeks	
ALT or AST >3x ULN and either TBL >2x ULN or INR >1.5	In participants with Gilbert's syndrome, doubling of direct bilirubin should be used for LY3209590 or insulin glargine interruption or discontinuation decisions rather than TBL>2x ULN.
ALT or AST >3x ULN with the appearance of fatigue, nausea, vomiting, right upper quadrant pain or tenderness, fever, rash, and/or eosinophilia (>5%)	

ALP >3x ULN, when the source of increased ALP is the liver	
ALP >2.5x ULN and TBL > 2x ULN	In participants with Gilbert's syndrome, doubling of direct bilirubin should be used for LY3209590 or insulin glargine interruption or discontinuation decisions rather than TBL >2x ULN.
ALP >2.5x ULN with the appearance of fatigue, nausea, vomiting, right upper quadrant pain or tenderness, fever, rash, and/or eosinophilia (>5%)	

Abbreviations: ALP = alkaline phosphatase; ALT = alanine aminotransferase; AST = aspartate aminotransferase; TBL = total bilirubin; ULN = upper limit of normal.

Resumption of the study intervention can be considered only in consultation with the Lilly-designated medical monitor and only if the liver test results return to baseline and if a self-limited, non-drug etiology is identified.

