### 8.2.5. Hepatic Monitoring

#### Close hepatic monitoring

##### *Initiating laboratory and clinical monitoring for abnormal liver laboratory test results*

Laboratory tests (Section 10.5), including ALT, AST, ALP, TBL, direct bilirubin, GGT, and creatine kinase, should be repeated within 48 to 72 hours to confirm the abnormality and to determine if it is increasing or decreasing, if 1 or more of these conditions occur.

If a participant with baseline results of...	develops the following elevations:
ALT or AST <1.5x ULN	ALT or AST $\geq$ 3x ULN
ALP <1.5x ULN	ALP $\geq$ 2x ULN
TBL <1.5x ULN	TBL $\geq$ 2x ULN (except for participants with Gilbert's syndrome)
ALT or AST $\geq$ 1.5x ULN	ALT or AST $\geq$ 2x baseline
ALP $\geq$ 1.5x ULN	ALP $\geq$ 2x baseline
TBL $\geq$ 1.5x ULN	TBL $\geq$ 1.5x baseline (except for participants with Gilbert's syndrome)

Abbreviations: ALP = alkaline phosphatase; ALT = alanine aminotransferase; AST = aspartate aminotransferase; TBL = total bilirubin; ULN = upper limit of normal.

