***What to do if the abnormal condition persists or worsens***

If the abnormality persists or worsens, clinical and laboratory monitoring, and evaluation for possible causes of abnormal liver tests should be initiated by the investigator in consultation with the Lilly-designated medical monitor. At a minimum, this evaluation should include physical examination and a thorough medical history, including

- symptoms
- recent illnesses, for example, heart failure, systemic infection, hypotension, or seizures
- recent travel
- history of concomitant medications, including over-the-counter, herbal and dietary supplements, and
- history of alcohol drinking and other substance abuse.

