***Frequency of monitoring***

Initially, monitoring of symptoms and hepatic biochemical tests should be done at a frequency of 1 to 3 times weekly, based on the participant's clinical condition and hepatic biochemical tests. Subsequently, the frequency of monitoring may be lowered to once every 1 to 2 weeks, if the participant's clinical condition and lab results stabilize. Monitoring of ALT, AST, ALP, and TBL should continue until levels normalize or return to approximate baseline levels.

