**Comprehensive hepatic evaluation**

***When to perform a comprehensive evaluation***

A comprehensive evaluation should be performed to search for possible causes of liver injury if 1 or more of these conditions occur:

If a participant with baseline results of...	develops the following elevations:
ALT or AST $<1.5 \times$ ULN	ALT or AST $\geq 3 \times$ ULN with hepatic signs or symptoms a , or ALT or AST $\geq 5 \times$ ULN
ALP $<1.5 \times$ ULN	ALP $\geq 3 \times$ ULN
TBL $<1.5 \times$ ULN	TBL $\geq 2 \times$ ULN (except for participants with Gilbert's syndrome)
ALT or AST $\geq 1.5 \times$ ULN	ALT or AST $\geq 2 \times$ baseline with hepatic signs or symptoms a , or ALT or AST $\geq 3 \times$ baseline
ALP $\geq 1.5 \times$ ULN	ALP $\geq 2 \times$ baseline
TBL $\geq 1.5 \times$ ULN	TBL $\geq 2 \times$ baseline (except for participants with Gilbert's syndrome)

Abbreviations: ALP = alkaline phosphatase; ALT = alanine aminotransferase; AST = aspartate aminotransferase; TBL = total bilirubin; ULN = upper limit of normal.

a Hepatic signs/symptoms are severe fatigue, nausea, vomiting, right upper quadrant abdominal pain, fever, rash, and/or eosinophilia  $>5\%$ .

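### One liver stopping rule needs an INR that Protocol 8.2.5 does not require until a higher ALT/AST level, so mainly between 3x and 5x ULN it rests on discretionary testing

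*Protocol*

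**What the plan says.** **Stopping rule (Protocol 7.1.1).** One row of the table reads "ALT or AST >3x ULN and either TBL >2x ULN or INR >1.5". An INR above 1.5 is therefore enough, with the transaminase elevation, even when bilirubin is not raised. Other rows stop drug without an INR: ALT or AST above 8x ULN, "ALT or AST >5x ULN for more than 2 weeks", and above 3x ULN with listed symptoms.

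**Work-up (Protocol 8.2.5).** Testing escalates in steps.

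- Close monitoring: "Laboratory tests (Section 10.5), including ALT, AST, ALP, TBL, direct bilirubin, GGT, and creatine kinase, should be repeated within 48 to 72 hours". Seven tests are named, and PT-INR is not one of them.
- If the abnormality persists or worsens, monitoring and a search for causes "should be initiated by the investigator in consultation with the Lilly-designated medical monitor". The stated minimum is an examination and a history.
- Continued follow-up: "Monitoring of ALT, AST, ALP, and TBL should continue until levels normalize or return to approximate baseline levels". Its frequency is initially 1 to 3 times weekly.
- Comprehensive evaluation: "A comprehensive evaluation should be performed to search for possible causes of liver injury if 1 or more of these conditions occur". PT-INR first appears as a required test here.

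**Elsewhere.** The laboratory table in Section 10.2 contains no coagulation test. The Section 10.5 hepatic panel lists PT-INR but refers the reader back to 8.2.5 for the choice of tests.

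**The concern.** A stopping criterion works only if the value that decides it is obtained. Here a site can follow 8.2.5 to the letter and still have no INR while ALT or AST is in the range where the INR stop applies.

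The INR half of the rule matters most in exactly this situation. With symptoms, or with bilirubin above 2x ULN, other criteria already stop drug. The INR adds protection for a participant who has no symptoms and little bilirubin rise but whose synthetic function is impaired. What is at stake is the safety of an occasional participant, not the efficacy analysis.

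**Working it through.** No planned figure is involved. The check compares the thresholds in 7.1.1 with those in 8.2.5.

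**Inputs**

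- INR stop: ALT or AST >3x ULN with INR >1.5 (7.1.1).
- Stops needing no INR: >8x ULN, and >5x ULN for more than 2 weeks (7.1.1).
- 48 to 72 hour repeat: from 3x ULN if baseline is <1.5x ULN, otherwise from 2x baseline (8.2.5).
- PT-INR required, no symptoms: from 5x ULN if baseline is <1.5x ULN, otherwise from 3x baseline (8.2.5).
- Highest ALT or AST allowed at screening: 3x ULN (5.2, criterion 22). I assume baseline does not exceed it.
- Participant has no symptoms, and TBL and ALP are below their own triggers.

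**Formulas.** Let b be baseline in multiples of ULN.

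- Repeat starts at 3 if b < 1.5, otherwise at 2b.
- INR is required from R = 5 if b < 1.5, otherwise R = 3b.
- Gap with no time limit: above 3 up to the lower of R and 5.
- Gap limited by the two-week stop: above 5 up to the lower of R and 8.

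**Results (multiples of ULN)**

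| Baseline b | Repeat starts | INR required from | Gap, no time limit | Gap limited to about two weeks | Above 3x with no required repeat |
|---|---|---|---|---|---|
| <1.5 | 3 | 5 | >3 to <5 | none | none |
| 1.5 | 2 × 1.5 = 3 | 3 × 1.5 = 4.5 | >3 to <4.5 | none | none |
| 2 | 2 × 2 = 4 | 3 × 2 = 6 | >3 to 5 | >5 to <6 | >3 to <4 |
| 2.5 | 2 × 2.5 = 5 | 3 × 2.5 = 7.5 | >3 to 5 | >5 to <7.5 | >3 to <5 |
| 3 | 2 × 3 = 6 | 3 × 3 = 9 | >3 to 5 | >5 to 8 | >3 to <6 |

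The two-week stop matters only when 3b > 5, that is b > 5/3 = 1.67. The >8x stop comes before the INR requirement when 3b > 8, that is b > 8/3 = 2.67. The two-week limit assumes the elevation is re-measured.

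**Does anything else require the INR?** Three routes could produce one: the open wording of the repeat-draw sentence with its pointer to Section 10.5, tests agreed with the medical monitor once the abnormality persists, and the general permission in 10.2 for the investigator to add tests. All three permit an INR. None requires it.

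**The case against.** **The plan already includes INR.** The list of repeat tests is introduced as non-exhaustive and cites Section 10.5, which lists PT-INR. This shows that the test is available, but not that it is required. Section 10.5 hands test selection back to 8.2.5. Adding PT-INR at the comprehensive evaluation would be redundant if it were already due at the repeat draw. Creatine kinase is likewise on the 10.5 panel and absent from scheduled chemistry; the repeat list names it and does not name INR.

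**Tiered testing is a design choice, and the band is supervised.** This largely stands. A participant who meets the repeat trigger is retested within 48 to 72 hours. If the abnormality persists, monitoring is initially 1 to 3 times weekly and the medical monitor is consulted. The investigator may also interrupt or stop drug on clinical judgment (7.1, 7.1.3).

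**Exposure is small.** This also stands. As far as the schedule can be read (its columns are displaced in the text available to me), routine chemistry falls at about one visit between randomization and Week 26. By Week 26 the last LY3209590 dose, at Week 25, has already been given.

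**Stronger readings a reader might infer.** One is that INR would never be obtained, or that these participants go unmonitored. The discretionary routes and the monitoring rules contradict both. Another is that for raised baselines the gap runs unchecked to 8x ULN. Above 5x ULN the two-week stop limits it.

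**Conclusion.** The two sections do not line up. 7.1.1 sets a numeric stop at ALT or AST above 3x ULN with INR above 1.5, and 8.2.5 does not require the INR until 5x ULN or 3x baseline in a participant without symptoms. The main gap is above 3x to below 5x ULN for baselines under 1.5x ULN, and above 3x to below 4.5x ULN at a baseline of 1.5x. For higher baselines it extends further, but above 5x ULN it is limited to about two weeks of sustained elevation.

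This is a minor clarification. The number affected cannot be derived from the documents. I expect it to be small, because criterion 22 excludes liver disease other than NAFLD, scheduled on-treatment chemistry is sparse, and several conditions must coincide with an INR above 1.5. No efficacy or noninferiority conclusion is touched. The point concerns the protocol text: the laboratory manual was not available and may already specify the test.

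**What to change.** 1. **8.2.5, repeat draw.** Add PT-INR to the tests named for the 48 to 72 hour repeat when the ALT or AST trigger prompted it. An isolated ALP or bilirubin trigger need not bring in INR.
2. **8.2.5, raised baselines.** For baseline ALT or AST of 1.5x ULN or more, require a repeat draw that includes PT-INR when ALT or AST is above 3x ULN and above baseline. The draw itself must be required, because at baselines above 1.5x the present repeat starts only at 2x baseline, for example 4x ULN at baseline 2x.
3. **7.1.1, anticoagulants.** State that an INR above 1.5 explained by anticoagulant therapy is assessed with the medical monitor and does not by itself trigger the stop. The exception column now covers only Gilbert's syndrome, where "doubling of direct bilirubin should be used for LY3209590 or insulin glargine interruption or discontinuation decisions". Section 5.2 does not exclude anticoagulant users, and no baseline INR is scheduled. Resumption is allowed "only if the liver test results return to baseline and if a self-limited, non-drug etiology is identified", a condition that fits poorly when the raised INR has nothing to do with the liver.

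The cost is one extra tube at a draw that already takes place, an occasional extra draw for raised baselines, one judgment call for anticoagulant users, and a matching line in the laboratory manual if it is not already there. No threshold changes, and no new assay is needed because PT-INR is already on the Section 10.5 panel. Concomitant medications are already collected (6.8).

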### 7.1.2. Hypersensitivity Reactions

If the investigator determines that a systemic hypersensitivity reaction has occurred related to study intervention administration, the participant may be **permanently discontinued** from the study intervention, and the sponsor's designated medical monitor should be notified.

If the investigator is uncertain about whether a systemic hypersensitivity reaction has occurred and whether discontinuation of study intervention is warranted, the investigator may consult the sponsor.

### 7.1.3. Temporary Discontinuation

#### Criteria for temporary discontinuation of LY3209590 or insulin glargine

The investigator may temporarily interrupt study treatment, due to an AE, clinically significant laboratory value, hospital visits, travel, or shortage of study treatment supply.

This will be allowed for up to 21 consecutive days for insulin glargine or 3 consecutive doses for LY3209590 at any time during the study. This information should be documented by the investigator.

#### Guidance when temporary discontinuation of LY3209590 or insulin glargine occurs

Every effort should be made by the investigator to maintain participants in the study and to restart LY3209590 or insulin glargine promptly, as soon as it is safe to do so.

Participants will continue their study visits and follow-up according to the SoA.

Participants should resume the dose prescribed before the temporary dosing interruption at the discretion of the investigator.

#### **Recording temporary discontinuation of LY3209590 or insulin glargine**

The dates of LY3209590 or insulin glargine interruption and restart must be documented in source documents and entered on the CRF.

Participant noncompliance should not be recorded as interruption of LY3209590 or insulin glargine on the CRF.

### **7.2. Participant Discontinuation/Withdrawal from the Study**

Discontinuation is expected to be uncommon.

A participant may withdraw from the study

- at any time at the participant's own request
- at the request of the participant's designee, for example, parents or legal guardian
- at the discretion of the investigator for safety, behavioral, compliance, or administrative reasons
- if enrolled in any other clinical study involving an investigational product, or enrolled in any other type of medical research judged not to be scientifically or medically compatible with this study
- if the participant, for any reason, requires treatment with a therapeutic agent that is prohibited by the protocol and has been demonstrated to be effective for treatment of the study indication. In this case, discontinuation from the study occurs prior to introduction of the new agent, and
- if a study participant is diagnosed with any type of diabetes mellitus other than T2D.

At the time of discontinuing from the study, if possible, the participant will complete procedures for an early discontinuation visit and posttreatment follow-up, as shown in the SoA.

If the participant has not already discontinued the LY3209590 or insulin glargine, the participant will be permanently discontinued from the LY3209590 or insulin glargine at the time of the decision to discontinue the study.

If the participant withdraws consent for disclosure of future information, the sponsor may retain and continue to use any data collected before such a withdrawal of consent. If a participant withdraws from the study, the participant may request destruction of any samples taken and not tested, and the investigator must document this in the site study records.

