### Primary estimand (for primary objective)

### ***United States registration***

The *primary* clinical question of interest is:

What is the treatment difference between LY3209590 and insulin glargine in change from baseline at Week 26 in HbA1c in study eligible participants regardless of treatment discontinuation for any reason or initiation of rescue therapy?

The ***treatment regimen estimand*** will be used for the primary objective and is described by the attributes in this table.

Treatment Regimen Estimand Attribute	Description
Treatment condition	randomized treatment regardless of treatment discontinuation or initiation of rescue therapy.
Population	targeted study population. See Section 9.2 for details.
Endpoint	change from baseline to Week 26 in HbA1c.
Remaining intercurrent events	none. The 2 intercurrent events, treatment discontinuation for any reason and initiation of rescue therapy, are addressed by the treatment condition of interest attribute.
Population-level summary	difference in mean changes between treatment conditions.

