#### **6.1.3. Rescue Therapy for Management of Participants with Severe, Persistent Hyperglycemia during the Treatment Period**

Participants in this clinical trial will be treated with basal insulin, that is, LY3209590 or insulin glargine, both in combination with prandial insulin lispro. Correction doses of insulin lispro can also be used.

An additional antihyperglycemic medication should be considered as rescue therapy if a participant develops severe, persistent hyperglycemia after randomization, based on meeting one of the criteria in this table, and in the absence of intercurrent cause of the hyperglycemia.

Average Fasting Glucose over 2-week Period	Timing of Events
>270 mg/dL (15 mmol/L)	From Visit 15 until Visit 17 (Weeks 12 to 16)
>240 mg/dL (13 mmol/L)	After Visit 17 until Visit 19 (Weeks 16 to 20)
>200 mg/dL (11 mmol/L)	After Visit 19 until Visit 23 (Weeks 20 to 26)

Investigators should first confirm that the participant is fully compliant with the assigned therapeutic regimen and that the participant does not have an acute condition causing severe hyperglycemia. If study basal and prandial insulin therapy are fully optimized, the investigator will decide, in consultation with the participant, on an appropriate intensification of therapy after considering relevant clinical criteria. Therapy intensification may include adjustment of concomitant antihyperglycemic medication, addition of a concomitant antihyperglycemic medication if taking <3 concomitant medications as per Section 6.8.3, or addition of a non-study insulin. Participants who receive a new intervention for hyperglycemia management should also continue administering study insulin therapy for the remaining period in the trial.

Participants who require a new non-study basal insulin intervention as rescue therapy for hyperglycemia management must discontinue study basal insulin therapy (LY3209590 or insulin glargine). The participant will remain in the study and follow procedures for the remaining study visits.

The investigator should ensure that the participant met the criteria for severe or persistent hyperglycemia before initiating rescue medicine and document this in the source files.

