**1.2. Study Design**

- Study BDCV is a Phase 3, multicenter, randomized, open-label, comparator-controlled study to evaluate the efficacy and safety of once-weekly basal insulin (LY3209590) compared to insulin glargine in participants with T2D who are on once- or twice-daily basal insulin and at least 2 injections per day of prandial insulin prior to entering the study.

- The study includes a 3-week screening/lead-in period, a 26-week treatment period, and a 5-week safety follow-up period.
- Participants will continue prior stable diabetes therapy with 0 to 3 allowed non-insulin antihyperglycemic medications during the study.
- Participants will discontinue their previous basal insulin doses at randomization and will be assigned to either LY3209590 or insulin glargine, and all participants will be treated with prandial insulin, insulin lispro.
- Assignment to treatment groups will be determined by an interactive web-response system (IWRS). Participants will be randomly assigned to 1 of the 2 treatment groups in 1:1 ratio (LY3209590: insulin glargine) at Week 0 (Visit 3). Stratification will be by country, HbA1c stratum at Week -3 (Visit 1) (<8.0%, ≥8.0%), and routine use of personal continuous glucose monitoring (CGM) or flash glucose monitoring (FGM) at randomization.
- This is a treat-to-target study, both treatment groups will undergo titration to achieve an FBG target within the range of 80-120 mg/dL,. The primary endpoint at Week 26 (Visit 23) is based on participants reaching a stable insulin dose in order to achieve glycemic stability approximately 12 weeks in advance of the 26-week primary endpoint. HbA1c is the primary endpoint and reflects glycemic control from the prior 8 to 12 weeks.
- Rescue therapy will be considered during the treatment period if the participants meet the protocol criteria of severe, persistent hyperglycemia.
- If study intervention is permanently discontinued, the participant will be encouraged to continue participation in the study for continued monitoring. Both efficacy (including HbA1c) and safety data will continue to be collected per the schedule of activities in the protocol.

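### Protocol 7.2 can end study follow-up when a prohibited glucose-lowering agent is needed, while 7.1 and the US treatment-regimen estimand expect follow-up to Week 26

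*Protocol*

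**What the plan says.** Protocol 7.2 gives a list of circumstances in which a participant may withdraw from the study. One is that the participant, whatever the cause, "requires treatment with a therapeutic agent that is prohibited by the protocol and has been demonstrated to be effective for treatment of the study indication". It continues: "In this case, discontinuation from the study occurs prior to introduction of the new agent". The same section adds that anyone leaving the study who is still on study basal insulin is permanently taken off it at that time. The bullet is repeated in the German text in Protocol 10.7.1.

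Protocol 7.1 covers permanent discontinuation of study basal insulin. After it, "the participant will remain in the study and follow procedures for remaining study visits, as shown in the SoA". It goes on: "Participants who stop LY3209590 or insulin glargine permanently may receive another glucose-lowering medication". No class is excluded there.

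The table in Protocol 6.8.3 marks insulin mixtures, sulfonylureas, thiazolidinediones, meglitinides and alpha-glucosidase inhibitors as not allowed in the treatment period and not allowed as rescue. It has no column for use after permanent discontinuation.

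For US registration the treatment condition of the primary estimand is "randomized treatment regardless of treatment discontinuation or initiation of rescue therapy". SAP 1.2 says of participants who permanently stop study intervention: "Both efficacy (including HbA1c) and safety data will continue to be collected per the schedule of activities in the protocol".

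**The concern.** Take a participant who permanently stops study basal insulin and is then moved to, say, an insulin mixture or a sulfonylurea. Protocol 7.1 keeps this person in the study with all remaining visits. The timing sentence in 7.2 has the person leave before the new agent starts. A site can defend either course, so whether a Week 26 HbA1c exists depends on which section it applies.

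This matters for the US primary analysis. SAP 4.3.2 names early study discontinuation as the source of missing Week 26 values. It imputes them from retrieved dropouts: participants in the same arm who stopped study intervention early but still have a Week 26 measurement. An exit under 7.2 therefore counts twice: one more value is missing and one possible donor is lost. Followed to the letter, 7.2 also means that no donor was ever observed on a prohibited agent, so the imputation model has no information on such patients. With fewer than 8 donors in either arm, the SAP switches to return-to-baseline multiple imputation.

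**Working it through.** **Passages side by side**

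| Question | Protocol 7.1 | Protocol 7.2 |
|---|---|---|
| Trigger | Permanent stop of study basal insulin | Need for a prohibited, effective agent |
| Another glucose-lowering agent? | May be given; no class limit | Only after leaving the study |
| In the study afterwards? | Yes, for the remaining visits | No |
| Wording | Declarative | Permissive opening, declarative timing sentence |

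Because 7.2 also ends study insulin, every exit under it is a treatment discontinuation. The US estimand says such participants are to be counted with the outcome they actually have. The efficacy estimand is hardly touched: SAP Section 3 cuts its data shortly after the last study dose or at rescue, so later values would not be used anyway.

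**The plan's own figures** (Protocol 9.5: 670 randomized 1:1, 15% dropout, SD 1.1, true difference 0, two-sided 95% CI)

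- Completers: 670 × 0.85 = 569.5, about 284 per arm.
- SE = 1.1 × √(2/284) = 0.0923.
- Power = Φ(margin/SE − 1.96): 99.1% at 0.4 and 90.1% at 0.3. Both stated figures reproduce.

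**Size, part 1: power.** The number of 7.2 exits is not given, so the shares below are assumed. They come on top of the 15%, with n per arm = 335 × (0.85 − extra share).

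| Extra share lost | n per arm | Power, margin 0.4 | Power, margin 0.3 |
|---|---|---|---|
| 0 | 284.8 | 99.1% | 90.2% |
| 1% | 281.4 | 99.1% | 89.9% |
| 2% | 278.1 | 99.0% | 89.5% |
| 5% | 268.0 | 98.8% | 88.4% |
| 10% | 251.2 | 98.3% | 86.4% |

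SAP 2.1 ties the 0.4% margin to the treatment-regimen estimand, so the 0.4 column is the relevant one.

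This table ignores the imputation. A simulation that includes it keeps donors plus missing at the planned 335 × 0.15 ≈ 50 per arm and starts, by assumption, from 25 donors and 25 missing. Moving 3 or 7 participants per arm (about 1% or 2%) from donor to missing leaves power at the 0.4% margin at about 98% to 99%.

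**Size, part 2: bias.** Let p be the share of an arm lost under 7.2 and d the true minus the imputed mean HbA1c in those lost. The bias in the treatment difference is about p_T × d_T − p_C × d_C. With the same d in both arms, assumed at 0.3 to 1.0 points:

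- 3% against 1% lost: 0.02 × 0.3 = 0.006, up to 0.02 × 1.0 = 0.02 points.
- 10% against 5% lost: 0.05 × 0.3 = 0.015, up to 0.05 × 1.0 = 0.05 points. This is about 4% to 12.5% of the 0.4 margin.
- Equal losses and equal d: zero.

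**The case against.** **The text can be read without conflict.** The 7.2 list opens permissively, so exit is not plainly compulsory. An agent that 7.1 lets a participant take after stopping study insulin is arguably not a prohibited agent, and 6.8.3 has no column that says otherwise. This stands in part. A reader might infer that a site cannot possibly comply with both sections, but the documents do not go that far. They do leave the site to decide, under a timing sentence worded as a rule, whether primary-endpoint data are collected.

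**Rescue basal insulin is not affected.** A reader might also infer a clash with Protocol 6.1.3, which says of participants who need non-study basal insulin as rescue: "The participant will remain in the study and follow procedures for the remaining study visits". It is not one. Note d to the 6.8.3 table expressly provides for that use and keeps the participant in the study, so the agent is not prohibited and 7.2 is not triggered. Metformin, GLP-1 receptor agonists, DPP-4 inhibitors, SGLT2 inhibitors and non-study prandial insulin are likewise allowed as rescue. The problem is confined to the five classes marked as not allowed.

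**The analysis plan anticipates missing data.** SAP 4.3.2 imputes it. SAP 4.3.3.1 adds a two-way tipping-point analysis and imputation under the noninferiority null. Protocol 7.2 asks for an early discontinuation visit where possible, and expects discontinuation to be uncommon. All this limits the consequence. But an exit visit held before the new agent starts does not supply a Week 26 value, and a sensitivity analysis cannot recover data that sites were told not to collect.

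**Conclusion.** The point holds as a conflict, or at the least an ambiguity, between Protocol 7.1 and 7.2 for participants who move to a class that 6.8.3 marks as not allowed. Read as a rule, 7.2 creates missing Week 26 HbA1c in participants whom the US estimand and SAP 1.2 intend to follow, and reduces the pool of retrieved dropouts.

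The numerical effect is probably small. It would matter if exits under this bullet were frequent or differed between arms, which is possible in an open-label trial but not something the documents quantify. The sizes above rest on assumed exit shares and on an assumed gap between true and imputed HbA1c.

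A reader might infer that losing donors would cut noninferiority power sharply. Imputation from very few donors does lose precision, but nothing in the documents suggests that 7.2 alone would bring the donor count that low. The case for a change rests on keeping data collection in line with the estimand, at little cost, and not on loss of power.

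**What to change.** Reconcile the 7.2 bullet, and its repeat in the German text in 10.7.1, with 7.1 and the 6.8.3 table. The sponsor should make clear whether the classes marked as not allowed still count as prohibited after permanent discontinuation of study insulin. This review takes no view on which treatments should be allowed.

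For data collection only, add a sentence that keeps starting another glucose-lowering agent separate from ending study follow-up: scheduled visits and the Week 26 HbA1c are still collected unless the participant withdraws from the study. This matches what 7.1 and SAP 1.2 already say, and no analysis method has to change.

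The cost is one bullet in a protocol amendment, repeated in the German text, and visits already in the schedule for what is likely to be a few participants.
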